Provide details of remuneration, when applicable. Even when subjects may derive medical benefit from participation, it is often the case that extra hospital visits, meals at the hospital, parking fees or other inconveniences will result in additional out-of-pocket expenses related to study participation. Investigators may wish to consider providing reimbursement for such expenses when funding is available

Each participating clinician will receive a \$5 gift card for each completed survey. This will provide incentive but not enough to be coercive for participation. We are currently submitting this to Research Compliance for approval, though anticipate approval due to similar approved approaches with prior research. For guidance, refer to the following Partners policies: Recruitment of Research Subjects https://www.partners.org/Assets/Documents/Medical-Research/Clinical- Research/Recruitment-Of-Research-Subjects.pdf

Guidelines for Advertisements for Recruiting Subjects https://www.partners.org/Assets/Documents/Medical-Research/Clinical- Research/Guidelines-for-Advertisements.pdf

Remuneration for Research Subjects

https://www.partners.org/Assets/Documents/Medical-Research/Clinical-Research/Remuneration-for-Research-Subjects.pdf

CONSENT PROCEDURES

Explain in detail how, when, where, and by whom consent is obtained, and the timing of consent (i.e., how long subjects will be given to consider participation). For most studies involving more than minimal risk and all studies involving investigational drugs/devices, a licensed physician investigator must obtain informed consent. When subjects are to be enrolled from among the investigators' own patients, describe how the potential for coercion will be avoided.

Consent procedures for patients - Because the intervention is not directly patient-facing, there will be no direct enrollment of eligible patients, and we will be requesting a waiver of written informed consent for patients.

Consent procedures for Admitting Clinicians – implied consent is obtained from the admitting clinicians as a function of filling out and submitting a survey response. All clinicians will be informed they have the right to opt out of any data collection activities at the beginning of the study and when requested to participate in these activities.

NOTE: When subjects are unable to give consent due to age (minors) or impaired decisionmaking capacity, complete the forms for Research Involving Children as Subjects of Research and/or Research Involving Individuals with Impaired Decision-making Capacity, available on the New Submissions page on the PHRC website:

https://partnershealthcare.sharepoint.com/sites/phrmApply/aieipa/irb

For guidance, refer to the following Partners policy: Informed Consent of Research Subjects: https://www.partners.org/Assets/Documents/Medical-Research/Clinical-Research/Informed-Consent-of-Research-Subjects.pdf

DATA AND SAFETY MONITORING

Describe the plan for monitoring the data to ensure the safety of subjects. The plan should include a brief description of (1) the safety and/or efficacy data that will be reviewed; (2) the planned frequency of review; and (3) who will be responsible for this review and for determining whether the research should be altered or stopped. Include a brief description of any stopping rules for the study, when appropriate. Depending upon the risk, size and complexity of the study, the investigator, an expert group, an independent Data and Safety Monitoring Board (DSMB) or others might be assigned primary responsibility for this monitoring activity.

NOTE: Regardless of data and safety monitoring plans by the sponsor or others, the principal investigator is ultimately responsible for protecting the rights, safety, and welfare of subjects under his/her care.

The principal investigator and data analyst will review all complaints and adverse events reported from patient and provider subjects each quarter. These will be reported to the study sponsor and Partners IRB annually or immediately if the complaint or adverse event is serious. In addition, the principal investigator and data analyst will review on a monthly basis adverse event rates, hospital length of stay, and 7-day readmission rates to ensure that the intervention itself is not causing harm compared with the pre-intervention period. If an increase in harm is suspected, we will report it to the IRB and take action as needed. Given the minimal risk of this study, we are not planning any automatic stopping rules or using a DSMB.

Describe the plan to be followed by the Principal Investigator/study staff for review of adverse events experienced by subjects under his/her care, and when applicable, for review of sponsor safety reports and DSMB reports. Describe the plan for reporting adverse events to the sponsor and the Partners' IRB and, when applicable, for submitting sponsor safety reports and DSMB reports to the Partners' IRBs. When the investigator is also the sponsor of the IND/IDE, include the plan for reporting of adverse events to the FDA and, when applicable, to investigators at other sites.

NOTE: In addition to the adverse event reporting requirements of the sponsor, the principal investigator must follow the Partners Human Research Committee guidelines for Adverse Event Reporting

See Above

MONITORING AND QUALITY ASSURANCE

Describe the plan to be followed by the principal investigator/study staff to monitor and assure the validity and integrity of the data and adherence to the IRB-approved protocol. Specify who will be responsible for monitoring, and the planned frequency of monitoring. For example, specify who will review the accuracy and completeness of case report form entries, source documents, and informed consent. NOTE: Regardless of monitoring plans by the sponsor or others, the principal investigator is ultimately responsible for ensuring that the study is conducted at his/her investigative site in accordance with the IRB-approved protocol, and applicable regulations and requirements of the IRB.

The principal investigator and study analyst will review the study database monthly during the data collection period to ensure data integrity. Additionally, survey collection directly into REDCap will ensure data integrity with limited opportunity for errors in data transfer. Protocols will also be monitored quarterly to ensure adherence to the study protocol as approved by the IRB.

For guidance, refer to the following Partners policies: Data and Safety Monitoring Plans and Quality Assurance https://www.partners.org/Assets/Documents/Medical-Research/Clinical-Research/DSMP-in- Human-Subjects-Research.pdf

Reporting Unanticipated Problems (including Adverse Events) https://www.partners.org/Assets/Documents/Medical-Research/Clinical- Research/Reporting-Unanticipated-Problems-including-Adverse-Events.pdf

PRIVACY AND CONFIDENTIALITY

Describe methods used to protect the privacy of subjects and maintain confidentiality of data collected. This typically includes such practices as substituting codes for names and/or medical record numbers; removing face sheets or other identifiers from completed surveys/questionnaires; proper disposal of printed computer data; limited access to study data; use of password-protected computer databases; training for research staff on the importance of confidentiality of data, and storing research records in a secure location.

NOTE: Additional measures, such as obtaining a Certificate of Confidentiality, should be considered and are strongly encouraged when the research involves the collection of sensitive data, such as sexual, criminal or illegal behaviors.

The data collected from providers will not have any identifiers and will not be coded except to track who has completed surveys (e.g., in order to send a reminder as needed). Patient identifiers (i.e., to connect survey data collected from providers with data abstracted from administrative data sources) will be kept in a separate, password-protected file. Any patient identifiers will be removed prior to any analysis, and results will only be presented in aggregate.

All data will be collected through REDCap, a secure, HIPAA compliant webbased application hosted by Partners, and only accessible to IRB-approved study staff. Additionally the iPad being used for this study will be linked to REDCap and will likewise be password protected.

All other files and electronic data will be stored on within databases in a shared file area within the Partners firewall on a Partners password-protected computer with anti-virus software. A database with the link from PHI (e.g., MRN) to subject ID number will be kept separate from the rest of the data. Only IRB-approved study staff trained in the protection of human subjects will have access to study data.

SENDING SPECIMENS/DATA TO RESEARCH COLLABORATORS OUTSIDE PARTNERS

Specimens or data collected by Partners investigators will be sent to research collaborators outside Partners, indicate to whom specimens/data will be sent, what information will be sent, and whether the specimens/data will contain identifiers that could be used by the outside collaborators to link the specimens/data to individual subjects.

N/A

Specifically address whether specimens/data will be stored at collaborating sites outside Partners for future use not described in the protocol. Include whether subjects can withdraw their specimens/data, and how they would do so. When appropriate, submit documentation of IRB approval from the recipient institution.

N/A

RECEIVING SPECIMENS/DATA FROM RESEARCH COLLABORATORS OUTSIDE PARTNERS

When specimens or data collected by research collaborators outside Partners will be sent to Partners investigators, indicate from where the specimens/data will be obtained and whether the specimens/data will contain identifiers that could be used by Partners investigators to link the specimens/data to individual subjects. When appropriate, submit documentation of IRB approval and a copy of the IRB-approved consent form from the institution where the specimens/data were collected.

N/A

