Of note, the shifting of responsibility of documentation of the new standardized accept note will not supplant the current role of the accepting clinician to make the clinical decision on acceptance or rejection of the transfer request. As is currently done, the Access Center nurse and accepting clinician participate in a conference call with the transferring clinician such that either can ask questions (and the Access Center nurse can hear all the answers and document them in the accept note template). In this way, the Access Center nurse can ensure that the minimum necessary information is collected and documented, while also including additional clinical information requested by the accepting clinician.

Aim 3. Prospectively evaluate the impact of the intervention on patient safety outcomes, including: clinician-reported medical errors and adverse events, length of stay after transfer, rapid-response or code within 6-hours of transfer, ICU-transfer within 24-hours of transfer, and 3-day and inhospital mortality.

Study Design: We will conduct a prospective 24-month interrupted time series (ITS) study during which we will implement the standardized accept note and evaluate impact on all measured outcomes post- versus pre-implementation, accounting for baseline temporal trends.

Setting, Subjects, Eligibility, Enrollment: Eligible patients will include any patient age 18 or older transferred from another acute care hospital to the GMS, cardiology, oncology or medical/cardiac ICU services at BWH during the study period. Because the intervention is not directly patient-facing, there will be no direct enrollment of eligible patients, and we will be requesting a waiver of written informed consent for patients (see Organizational Internal Review Process, above). Thus, all eligible patients transferred during the study period will be in the study.

Instruments, Tests and/or Measurements: A trained research assistant (RA) will conduct surveys of admitting clinicians within 48-hours after IHT patient admission to obtain clinician- reported medical errors and adverse events, including medical errors resulting in patient harm (e.g., preventable and

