8) Mortality, including 3-day mortality (within 3 days of transfer) and inhospital mortality (secondary outcome)

9) Intermediate process outcomes, including presence, timeliness and completeness of accept note as measured by frequency of accept note availability at time of IHT patient arrival and frequency of inclusion of prespecified data elements (secondary outcome)

Statistical Methods and Analytic Plan: All outcomes will be compared postversus pre-implementation via ITS methodology, allowing us to evaluate for statistically significant changes in outcomes while accounting for baseline trends. Multivariable analyses will be utilized to adjust for potential confounders.

Covariates: Potential confounders will be collected via administrative sources and include basic patient demographics (age, gender, race, ethnicity), insurance, diagnosis category (using standard ICD-10 grouper algorithms on the principal problem on the Hospital Problem List on admission, which we have found to be more accurate than the billing diagnosis on admission), comorbidity (i.e., Elixhauser score), illness severity (eCART score on admission, which uses vital sign and laboratory data to predict cardiac arrest, ICU transfer, or death among hospitalized patients),36 clinical service at time of admission, and time of year of transfer (by quarter) to adjust for training effects on residents and seasonal case mix. To avoid over-testing, all patient characteristics will be entered into the analysis model. Nonsignificant collinear terms will be removed from the final models.

Subgroup analysis: We will conduct a limited number of a priori subgroup analyses to evaluate for differential effect of the intervention in different sub-populations of transferred patients by using interaction terms (subgroup*intervention) to determine effect modification. Specifically, we will stratify analyses by: 1) admitting service (GMS, cardiology, oncology, medical/cardiac ICU); 2) diagnosis category; and 3) severity of illness on admission (using the eCART score as described above).

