Statistical techniques: For all analyses we will use a segmented regression analysis on all eligible patients, evaluating outcomes monthly during the preimplementation and post-implementation periods (after the 3-month "washin" period). This approach quantifies both a "step" change in the level of outcome and a "slope" change in the trend of outcome. For our primary outcome (number of clinician-reported medical errors per patient), we will use multivariable Poisson regression models (SAS v9.4 statistical package, Cary, NC). For adverse events, preventable and ameliorable adverse events, and other dichotomous outcomes (rapid response/code, ICU-transfer, mortality, presence of accept note) we will use multivariable logistic regression models. For LOS, given its skewed nature we will use a multivariable generalized linear regression model assuming a gamma distribution with a log-link. We will use descriptive statistics to evaluate timeliness of accept note availability and inclusion of accept note data elements. For all analyses, the transfer episode will serve as the unit-ofanalysis.

Outcomes reporting: Patient and transfer process characteristics will be presented descriptively using means with standard deviations, medians with

inter-quartile ranges, and proportions with 95% confidence intervals as appropriate. Each outcome will be reported as crude as well as adjusted and clustered effects with 95% confidence intervals. All analyses will be on an intention-to-treat basis. Two-sided p values < 0.05 will be considered significant. All analyses will be conducted using SAS (SAS v9.4 statistical package, Cary, NC).

Power and sample size: Based on previous data, we estimate a baseline rate of 25 reported medical errors per 100 patient transfers. With an alpha of 0.05, we will require an effective sample size of approximately 594 patient transfers during the 9-month pre-implementation period and 594 patients transfers during the 9-month post-implementation period to have 80% power to detect a 30% relative reduction to 17.5 errors per 100 patient transfers, as has been observed in similar studies. Assuming 1,848 total patient transfers to GMS, cardiology, oncology and medical/cardiac ICU services at BWH per year (1,368 per 9-months, internal data), while allowing for missed days of survey administration (i.e., during holidays), and accounting for a survey response rate of 90% (based on similar studies), we should easily achieve this sample size.

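### The rule that drops nonsignificant collinear terms selects covariates on outcome p-values, can remove calendar quarter, and does not expressly protect the trend terms

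*Protocol*

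**What the plan says.** The Covariates paragraph of Aim 3 lists the potential confounders. Besides demographics, insurance, diagnosis category, comorbidity, illness severity and clinical service, the list includes "time of year of transfer (by quarter) to adjust for training effects on residents and seasonal case mix". It continues: "To avoid over-testing, all patient characteristics will be entered into the analysis model". The next sentence is the rule at issue: "Nonsignificant collinear terms will be removed from the final models".

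The time structure is set elsewhere. Study Design promises to "evaluate impact on all measured outcomes post- versus pre-implementation, accounting for baseline temporal trends". The Statistical Methods and Analytic Plan paragraph describes the method as "allowing us to evaluate for statistically significant changes in outcomes while accounting for baseline trends". Statistical techniques prescribes segmented regression for all analyses and says "This approach quantifies both a 'step' change in the level of outcome and a 'slope' change in the trend of outcome". For the primary outcome, "we will use multivariable Poisson regression models". Under Outcomes reporting, "Two-sided p values < 0.05 will be considered significant".

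No sentence defines collinear, gives a p-value for removal, or names terms that must stay.

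**The concern.** Two consecutive sentences pull in opposite directions. The first enters all patient characteristics to avoid over-testing. The second tests them against the outcome and deletes some. The final model is then read as though it had been chosen in advance, so its interval carries none of the selection uncertainty.

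The sharper problem is what the rule selects on. Collinearity inflates a term's standard error, so a collinear term tends to be nonsignificant even when its effect is real. Quarter is in the covariate list, and in a short segmented series it is collinear with time and step. It would usually be removed because 9 + 9 months cannot estimate it, not because season has been shown to be absent.

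If a seasonal pattern exists and quarter is gone, the model reads a rise or fall across the quarters of each segment as a time trend. It extrapolates that trend over the wash-in and charges the discrepancy to the step. The result can be a false benefit or a false harm, on the primary outcome and on every modelled secondary outcome.

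**Working it through.** **Inputs from the protocol.** 9 months before, a 3-month wash-in that is not analysed, and 9 months after; 1,848 transfers a year; 90% survey response; 0.25 errors per transfer at baseline; target 0.175 (rate ratio 0.70); two-sided 0.05; 594 transfers per period.

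**Assumptions, not in the protocol.** Size and shape of any season; the start month; removal of quarter when its joint p-value is 0.05 or more.

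**The protocol's own figure.** For two Poisson rates, n = (1.960 + 0.842)² × (0.25 + 0.175) / (0.25 − 0.175)² = 7.849 × 0.425 / 0.005625 ≈ 593.0, rounded up to 594. It reproduces, and it is a plain two-period comparison with no trend and no quarter.

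**Volume.** 1,848 × 9/12 = 1,386 (the protocol prints 1,368; the difference does not matter here). 1,386 × 0.9 ≈ 1,247 surveys per period, or 138.6 a month, before missed days.

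**Collinearity.** With months 1–9 and 13–21, step and time correlate at 0.92. If month 1 opens a calendar quarter, the variance inflation factors are 70.4 for time, 55.6 for step, 4.4 for slope change, and 4.3 and 13.3 for the two quarter dummies. If it does not, all four quarters occur and the three quarter dummies range from 4.4 to 21.8.

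**Type I error of the step.** Segmented Poisson regression with about 1,247 surveys per period and no intervention effect; only quarter may be removed; at least 2,000 runs per scenario. Ranges combine separate runs.

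| Assumed season across quarters | Start | Quarter dropped | Step rejects | Mean rate ratio |
|---|---|---|---|---|
| None | aligned or shifted | about 95% (aligned) | about 5–8% | – |
| Mid-period peak of 10% or 20% | aligned | – | about 5–6% | – |
| Monotone 5%/10% | aligned or shifted | – | about 9–16% | – |
| Fall of 10%/20% | aligned | 91–92% | 40–43% | 1.35–1.38 |
| Rise of 10%/20% | aligned | 92% | 37–38% | 0.77–0.78 |
| Log-rate +0.1, 0, −0.1 | aligned | 92% | 39% | – |
| Same | shifted 1 month | – | 22% | – |
| Same | shifted 2 months | – | 11% | – |

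With every term kept, the step test rejected in about 4–6% of runs throughout. The removal rate of 80–96% covers the no-season and monotone scenarios; 80% belongs to a steeper pattern of ±0.2 on the log scale. A strong mid-period peak is detected and kept more often. When the start is shifted, the level of the fourth quarter must also be assumed. For the 10%/20% fall, that gives about 24–38% at one month and 12–29% at two.

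**Precision of the step at about 1,247 per period.** The first standard error assumes no effect. The second assumes the target rates, with |ln 0.70| = 0.357.

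| Model | SE, no effect | SE, target rates | Power for a 30% step |
|---|---|---|---|
| Two-period comparison | – | 0.088 | about 98% |
| Step, trend, slope change | 0.21 | 0.223 | about 36–39% |
| The same plus quarter dummies | 0.60–0.69 | 0.645 (aligned) | about 8–9% |

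**The case against.** The strongest reply is that the sentence was never aimed at the time structure. It sits in the confounder paragraph, directly after a sentence on patient characteristics. Its ordinary purpose would be to prune overlapping measures, such as a comorbidity score against an illness-severity score.

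Much of this stands. A reader might infer that the rule strikes the baseline trend from the model. The documents do not support that: trend and slope change are not in the covariate list, and Study Design, the analytic plan and Statistical techniques all commit to them. Read that widely, the rule could also delete the step itself, whose variance inflation factor is 55.6, and nobody can have meant that. The supportable point is that these terms are not expressly protected.

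A reader might also infer that dropping quarter returns the study to an unadjusted comparison. It does not. Step, trend, slope change and the other covariates remain, and months 1–9 and 13–21 are the same calendar months, so the periods are balanced on season. What is left is distortion of the extrapolated step.

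Nor can one say without conditions that the test rejects far more often than 5%. The large figures need a monotone season, and the largest also need a start aligned to the calendar quarter. The protocol gives no seasonal size, shape or start month.

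What the reply does not remove is that quarter is in the list, the rule chooses on outcome p-values, and its criteria are undefined. The protocol itself regards season and training effects as worth adjusting for.

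**Conclusion.** The point holds in limited form. The protocol states a covariate-selection rule driven by outcome p-values. That rule can remove its own seasonal adjustment, and usually would in this layout if there were no season or a monotone one. It leaves the trend and slope terms without express protection.

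The consequence for the step test depends on facts the protocol does not give. Inflation is slight, to about 5–8%, with no season or with a mid-period peak in quarter-aligned months. It is about 9–40% for monotone patterns of 5–20%, falling as the start month moves off the quarter boundary. In the aligned 10%/20% rise, the spurious rate ratio of 0.77–0.78 is not far from the 0.70 the study is designed to detect.

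These figures assume Poisson counts, about 1,247 surveys per period, removal at p of 0.05 or more, and no other covariates. They show what the rule can do, not what it will do in this study.

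**What to change.** Replace the removal sentence with wording such as:

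> Time, step and slope-change terms stay in every model whatever their p-value. Calendar quarter and the listed confounders are not removed on outcome p-values. Any simplification for collinearity (merging categories, choosing one of two overlapping measures, or a more economical seasonal term) is decided from the covariate data alone, before outcome data are read, and is the same for all outcomes.

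The edit is small, but its statistical cost is not. Keeping quarter as dummies roughly triples the standard error of the log step (0.645 / 0.223 ≈ 2.9) and leaves about 8–9% power for a 30% step, against about 36–39% with the segmented terms alone. That lost precision was available only by taking season to be zero.

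For this reason the wording allows a more economical seasonal term, chosen without sight of outcomes. Power and sample size should also state the expected precision of the segmented model actually planned, because 594 per period describes a two-period comparison only.

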ameliorable adverse events). The RA will use a central patient report derived from our EHR system that lists all transferred patients to included services on a daily basis Monday through Friday (including weekend transfers on Mondays) and will perform targeted EHR review to determine the admitting clinician for each patient. The RA will then email that clinician a link and instructions to complete a short survey via REDCap, a free, secure, HIPAA compliant web-based application hosted by Partners (see included "DirectedEmailSurvey1"). Survey guestions, based on those from similar studies conducted by our group for other types of care transitions, will pertain to the clinician's care of the specific transferred patient and will ask about failures in communication (i.e., the presence of inaccurate or missing information, including missed or delayed diagnoses) and evaluate for any failures or delays in ordering or interpreting diagnostic studies, and delays in therapeutic care. The survey also asks about any adverse event (i.e., patient harm due to medical care), the severity of the event, and whether it was preventable or ameliorable (see "Appendix.ClinicianSurvey"). The RA will send 2 follow-up emails over the following 3 days (see "DirectedEmailSurvey.FollowUp"). After 3-days, any non-responding clinician will be contacted by the RA to conduct an in-person survey using an iPad linked to REDCap to improve response rate. All clinicians will be informed they have the right to opt out of any data collection activities at the beginning of the study and when requested to participate in these activities. Each participating clinician will receive a \$5 gift card for each completed survey (currently submitting to Research Compliance for approval). All other outcome measures will be obtained via administrative data with help from a database analyst.

Primary and Secondary Outcome Measures:

1) Clinician-reported medical errors (primary outcome), measured as the total number of medical errors per patient

- 2) Presence of any adverse event after transfer (secondary outcome)
- 3) Preventable adverse event after transfer (secondary outcome)
- 4) Ameliorable adverse event after transfer (secondary outcome)
- 5) Length of stay of hospitalization after transfer (secondary outcome)

6) Rapid-response (i.e., "pre-code") or code within 6 hours of transfer (secondary outcome)

7) ICU-transfer within 24 hours of transfer (secondary outcome, excluding ICU patients)

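### The primary outcome gets two intervention coefficients, each open to p<0.05, with no decisive test named, while the sample size assumes one hypothesis at alpha 0.05

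*Protocol*

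**What the plan says.** All of the relevant text is in the Protocol under Aim 3.

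- *Primary and Secondary Outcome Measures* gives a single primary outcome: "Clinician-reported medical errors (primary outcome), measured as the total number of medical errors per patient". Every other outcome is labelled secondary.
- *Statistical Methods and Analytic Plan* gives the purpose of the interrupted time series as "allowing us to evaluate for statistically significant changes in outcomes while accounting for baseline trends".
- *Statistical techniques* sets segmented regression on monthly data, leaving out a 3-month wash-in. For the primary outcome, "we will use multivariable Poisson regression models". It adds: "This approach quantifies both a 'step' change in the level of outcome and a 'slope' change in the trend of outcome".
- *Outcomes reporting* gives one rule for everything: "Two-sided p values < 0.05 will be considered significant".
- *Power and sample size* starts from a baseline: "we estimate a baseline rate of 25 reported medical errors per 100 patient transfers". It continues: "With an alpha of 0.05, we will require an effective sample size of approximately 594 patient transfers during the 9-month pre-implementation period", with the same number afterwards, "to have 80% power to detect a 30% relative reduction to 17.5 errors per 100 patient transfers".

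The protocol does not say which of the two coefficients, or which joint test or combined contrast, decides the primary claim. It does not say from which month the slope term is counted.

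**The concern.** A segmented model splits the intervention effect into a change of level and a change of trend. Each gets an estimate and a p value. With one unqualified threshold, a significant result on either can be presented as a significant change in the primary outcome, so the outcome has two chances at 0.05 where the sample size allows for one.

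Two further things are left open. The estimates can point in opposite directions, such as a favourable step with a worsening trend, and nothing says which would decide. The step also has no fixed meaning until the time origin is set, because it is the gap between the two fitted lines at that origin. A different origin gives a different step estimate and p value from the same data. With both the coefficient and its origin open, the primary test could be chosen after the data are seen.

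The *Expected Benefits* section says that a positive result would support adoption at other insured institutions. A claim of that kind needs one test stated in advance.

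**Working it through.** **1. The plan's own sample size.** Inputs from *Power and sample size*: rates 0.25 and 0.175 errors per transfer, alpha 0.05, power 80%. For two Poisson rates, two-sided:

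n = (z₀.₉₇₅ + z₀.₈₀)² × (λ₁ + λ₂) / (λ₁ − λ₂)² = (1.960 + 0.842)² × 0.425 / 0.075² = 593.03, rounded up to 594.

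This matches the stated 594. Alternatives do not: 600 on the log-rate scale, 589 on the square-root scale, 466 for two proportions, 468 for a one-sided Poisson test. The powered test is therefore one pre-versus-post contrast at a single alpha of 0.05. It treats the reduction as one constant difference between periods. Under such an effect the step equals ln(0.70) = −0.357 and the slope change is zero.

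**2. Correlation of step and slope estimates under no effect.** Assumed design: months 1–9 before, months 10–12 left out, months 13–21 after; equal weight per month; no covariates. The period means of time are 5 and 17, and each period has a sum of squares of time of 60. With the slope term counted from month c, in units of the monthly variance:

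- Var(slope change) = 1/60 + 1/60 = 1/30
- Var(step) = 2/9 + (c − 5)²/60 + (c − 17)²/60
- Cov = (c − 5)/60 + (c − 17)/60 = (c − 11)/30

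At c = 13: Var(step) = 0.2222 + 64/60 + 16/60 = 1.5556 and Cov = 2/30 = 0.0667, so r = 0.0667 / √(1.5556/30) = 0.293.

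**3. Probability that at least one |z| exceeds 1.96** (bivariate normal with correlation r):

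| Slope origin (month) | r | Either coefficient at p<0.05 |
|---|---|---|
| 9 | −0.293 | 9.5% |
| 9.5 (start of implementation) | −0.224 | 9.6% |
| 10 | −0.151 | 9.7% |
| 11 (middle of the gap) | 0 | 9.75% |
| 12 | 0.151 | 9.7% |
| 12.5 (end of wash-in) | 0.224 | 9.6% |
| 13 (first month after wash-in) | 0.293 | 9.5% |
| 17 (middle of the post period) | 0.676 | 8.5% |
| 21 (last month) | 0.837 | 7.6% |
| 0 (uncentred) | −0.860 | 7.4% |

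The ceiling is the independent case, 1 − 0.95² = 9.75%.

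**4. Simulation check.** Poisson data with no effect, 137 transfers per month at 0.25 errors each, 4,000 runs per coding: 9.45% (origin 9), 9.5% (origin 12) and 10.45% (origin 13). The simulation error is about √(0.095 × 0.905/4000) = 0.46 percentage points, so the last value lies about two standard errors above 9.5%. In that run the single-coefficient rates were also a little high, at 5.55% and 5.7%.

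**5. Other decision rules.** If one named coefficient or one joint 2-df test decides, the rate is 5%. If both coefficients must be significant, it is below 5%. If alpha is split at 0.025 each, the plan's own formula gives (2.241 + 0.842)² × 0.425 / 0.075² = 718.2, or 719 per period instead of 594.

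**The case against.** The strongest reply is that the protocol says the method *quantifies* a step and a slope. That describes what is estimated; it is not a success rule. A reader might infer that the trial's false-positive rate simply is about 9.6%. The documents do not support that: no sentence says that either coefficient alone establishes the primary claim, and no time coding is fixed. This part of the objection stands, and the figures above are conditional for that reason.

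A second reply is that the choice of contrast within a named model commonly goes in a statistical analysis plan, which may exist. That is fair as far as silence goes. But this protocol itself fixes the model, the threshold and the sample size, and those three do not fit together: one hypothesis at one alpha is powered, while two coefficients fall under the same unqualified threshold.

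A reader might also multiply the two coefficients across all ten modelled outcomes and infer a large overall false-positive probability. The documents do not support that either. The other outcomes are already labelled secondary. Several overlap, such as any, preventable and ameliorable adverse events, or 3-day and in-hospital mortality, so a calculation that assumes independence does not apply.

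Finally, the step is not the only possible choice: a joint test or a contrast averaged over the post months would also restore 5%. Nor can the choice be settled by power figures from a model without covariates, because the protocol plans to adjust for quarter of the year, which changes the precision of these contrasts.

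**Conclusion.** The point holds in conditional form. For its single primary outcome the protocol yields two coefficients, applies p<0.05 to both, and names neither a decisive test nor a time origin. The sample size allows for one hypothesis at 0.05. If either coefficient counts as a positive result, the false-positive rate is about 9.5% to 9.75% for origins from month 9 to month 13, and about 7.4% to 8.5% for the other codings examined. All of these exceed 5%.

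The figures assume equal monthly numbers, a 9 + 3 + 9 month layout, no covariates and approximately normal test statistics. Covariates would change the correlation. For jointly normal statistics, though, the either-coefficient rate cannot exceed 9.75%, and it exceeds 5% unless the two estimates are perfectly correlated.

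This is more than wording, because naming the test restores the error rate that the sample size assumes and removes a choice after the data are seen. It is not evidence that the trial's error rate is already inflated.

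**What to change.** Name one primary contrast and fix its time origin. One form that matches the planned constant reduction is:

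> The primary test is the adjusted step change in clinician-reported medical errors, expressed as the rate ratio at the first month after wash-in with time centred at that month, at two-sided 0.05. The slope change is reported with its 95% confidence interval as a secondary result and cannot by itself establish the primary claim.

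If the sponsor prefers a joint test or an averaged post-period contrast, that also holds 5%, provided it is named before the outcome data are analysed.

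The cost is a few sentences and no extra data. The downside is that an effect appearing only as a slope change can no longer be claimed as the primary result. The change does not make 594 the right number for the step: it was derived for a simple two-rate comparison, and power for whichever contrast is chosen should be checked in the model as planned, including the quarter adjustment.
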